6.2 Secondary outcome 2. Safety of intranasal heparin

To test the safety of intranasal heparin for treatment of adult and child outpatients with SARS-CoV-2 infection

Measure

2.1 The number of participants who discontinue treatment prior to day 10 from randomisation as a measure of treatment tolerability

Estimand

Population: Household members (older than 5 years) prescribed study drug, regardless of SARS-CoV-2 infection status (all enrolled participants)

Treatment: Unfractionated intranasal heparin 1400u each nostril (as heparin solution 5,000u/ml, 140microL/ actuation, TWO actuations each nostril) THREE times daily via a plastic nasal inhalator device or saline control **Outcome**: The number of participants who discontinue treatment prior to day 10

Summary measure: Proportion in each arm, with 95% confidence interval. **Potential intercurrent events**: None identified

No statistical comparison will be made between the treatment arms. We will simply provide the proportion, with a 95% confidence interval, adjusted for clustering by household.

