2.2. Secondary objectives

1. To test the efficacy of intranasal heparin to reduce SARS-CoV-2 viral shedding over 10 days from day of positive swab (health professional collected swab day 3 and 5, and day 10)

Measure:

- 1.1. Total number of index cases and household contacts combined (nasopharyngeal swab positive on day 1), who remain swab positive on day 3
- 1.2. Total number of index cases and household contacts combined (nasopharyngeal swab positive on day 1), who remain swab positive on day 5
- 1.3. Total number of index cases and household contacts combined (nasopharyngeal swab positive on day 1), who remain swab positive on day 10
- 1.4. Time to swab negative based on health care provider collected nasal swab for household members (index cases and household contacts) who were swab positive on day 1 by PCR
- 1.5. Mean Ct values on days 3, 5 and 10
- 1.6. Lowest Ct value amongst household members who become positive during the first 10 days
- 2. To test the safety of intranasal heparin for treatment of adult and child outpatients with SARS-CoV-2 infection.

Measure:

2.1 The number of participants who discontinue treatment prior to day 10 from randomisation as a measure of treatment tolerability

2.2: Listing of adverse events and serious adverse events

3. To test whether intranasal heparin administration reduces symptomatic disease in index cases and household contacts.

Measure:

3.1 Number of household contacts (swab negative on day 1 of study) becoming symptomatic of COVID-19 in the next 28 days

Symptomatic COVID-19 is defined as:

- Fever or chills PLUS ≥1 respiratory symptom (sore throat, cough, shortness of breath);
- OR 2 respiratory symptoms (sore throat, cough, shortness of breath);
- OR 1 respiratory symptom (sore throat, cough, shortness of breath) PLUS ≥2 non-respiratory symptoms (chills, nausea, vomiting, diarrhea, headache, conjunctivitis, myalgia, arthralgia, loss of taste or smell, fatigue or general malaise).

3.2 Time to symptom resolution for index case and household contacts who were SARS-CoV-2 positive on day 1, during the study period as measured with daily symptom diary until day 28

- Common symptoms included in the symptom diary:
- Fever or chills
- Cough
- Shortness of breath or difficulty breathing
- Fatigue
- Muscle or body aches
- Headache
- New loss of taste or smell
- Sore throat
- Congestion or runny nose
- Nausea or vomiting
- Diarrheoa
- 4. To test the impact of intranasal heparin on peak severity of illness.

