7. SAFETY OUTCOMES

Adverse events and serious adverse events will be summarised by treatment arm.

The following adverse events and reactions were reported:

 Major bleeding or clinically relevant non major bleeding as defined by The International Society on Thrombosis and Haemostasis (ISTH) for clinical trials involving anticoagulant drugs (Kaatz S, Ahmad D, Statistical Analysis Plan

- Nasal itching
- Any nose bleeding (free flowing blood vs not)
- HIT, which is an unexplained fall in platelet count and a positive heparin antibody test
- Local nasal irritation
- Local or generalised oedema
- Thrombosis
- Sneezing
- Other adverse events and reactions that, in the site Principal Investigator's (PI) judgement, are not part of the expected clinical course and could be related (at least possibly) to the study and are medically significant or had serious sequelae

Nose bleeds will be further described by providing the mean duration of nose bleeds.

All adverse events and serious adverse events will be listed by treatment arm using the population of household members (older than 5 years) prescribed study drug, regardless of SARS-CoV-2 infection status (all enrolled participants)

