	covariates			
Day 3	Risk difference			
	Risk ratio			
Day 5	Risk difference			
	Risk ratio			
Day 10	Risk difference			
	Risk ratio			
	Repeat for			
	Complete case analysis			
	without covariates			
	Analysis using multiple			
	imputation			
	Hypothetical estimand			

Table 11: Secondary outcome 1: Time to swab negative

	Heparin	Placebo	Hazard ratio (95% CI)
Median (95% CI)			-

Table 12: Secondary outcome 2: Safety of intranasal heparin

	Heparin	Placebo
Number discontinued treatment prior to day 10	N (%) 95% CI	

Table 13: Secondary outcome 3.1: Reduction of symptomatic disease

	Percentag positive N	e testing (%) 95% Cl	Comparison between arms (95% CI)
	Heparin	Placebo	
Treatment policy estimand			
Complete case analysis with covariates			
Risk difference			
Risk ratio			
Complete case analysis without covariates			
Risk difference			
Risk ratio			
Analysis using multiple imputation			
Risk difference			
Risk ratio			

Table 14: Secondary outcome 3.2: Reduction of symptomatic disease

Repeat Table 11

Table 15: Secondary outcomes 4.1 and 4.2: Hospitalisations

		Percentage N (%) 95% (-	Comparison between arms (95% Cl)
		Heparin	Placebo	
Household members				-
	Risk difference	-	-	
	Risk ratio	-	-	
Household members				-
	Risk difference	-	-	
	Risk ratio	-	-	

Table 16: Secondary outcome 4.1: Impact on peak severity of illness (maximum severity score) mean (95%CI)

Heparin	Placebo	Mean difference (95% CI)

Table 17: Secondary outcome 5.1.1. Neurological long COVID at 6 months. Presence of symptoms

	Heparin N (%)			Placebo N (%)				Overall odds ratio	
Symptom	Not present	Mild	Moderate	Severe	Not present	Mild	Moderate	Severe	
Fatigue									
Malaise									
Daytime									
tiredness									
etc									

Table 18: Secondary outcome 5.1.1. Neurological long COVID at 6 months. Presence of symptoms insubgroup of participants who had SARS-CoV-2 infectionRepeat Table 17

Table 19: Secondary outcome 5.1.2. Neurological long COVID at 6 months. Continuous neurological longCOVID score

	Heparin	Placebo	Mean difference (95% CI)
All participants			
Subgroup of			
participants who			
had SARS-CoV-2			
infection			

Table 20: Secondary outcome 5.1.3. Neurological long COVID at 6 months. Presence of symptoms

		SARS-C	oV-2 positive	2	SARS-CoV-2 negative				Overall odds ratio
Symptom	Not present	Mild	Moderate	Severe	Not present	Mild	Moderate	Severe	
Fatigue									
Malaise									
Daytime									
tiredness									
etc									

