Table 21: Secondary outcome 5.1.4. Neurological long COVID at 6 months. Continuous neurological longCOVID score

Heparin	Placebo	Mean difference (95% CI)

Table 22: Secondary outcome 5.1.5. Neurological long COVID at 6 months

Scale	Mear	n (95% CI)	Mean difference between arms (95% CI)	p-value
	Heparin	Placebo		
e.g. WAIS digit span				
DASS etc				
Repeat for subgroup of participants SARS-CoV2 positive				

Table 23: Secondary outcome 5.1.6. Neurological long COVID at 6 months.

Scale	Mean (95% CI)		Mean difference (95%	p-value
			CI)	
	SARS-	SARS-CoV-		
	CoV-2	2 negative		
	positive			
e.g. WAIS digit span				
DASS etc				
Repeat for subgroup of participants SARS-CoV2				
positive				

Table 24: Secondary outcome 5.1.6. Neurological long COVID at 6 months. Subgroup analysesRepeat Table 22 for each subgroup, also include p-value for subgroup

Table 25: Secondary outcome 5.2.1. Neurological long COVID at 6 months. Presence of symptomsRepeat Table 17

Table 26: Secondary outcome 5.2.1. Neurological long COVID at 6 months. Presence of symptoms insubgroup of participants who had SARS-CoV-2 infectionRepeat Table 18

Table 27: Secondary outcome 5.2.2. Neurological long COVID at 6 months. Continuous neurological long COVID score

Repeat Table 19

Table 28: Secondary outcome 5.2.3. Neurological long COVID at 6 months. Presence of symptomsRepeat Table 20

Table 29: Secondary outcome 5.2.4. Neurological long COVID at 6 months. Continuous neurological long COVID score Repeat Table 21

Table 30: Secondary outcome 5.2.5. Neurological long COVID at 6 months.Repeat Table 22

Table 31: Adverse events

	Heparin n (%)	Placebo n (%)
Major bleed		
Nasal itching		
Nose bleed		
HIT		
Local nasal irritation		
Loal or generalized oedema		
Thrombosis		
Sneezing		
Other		
Serious adverse events		
Mean duration of nose bleeds

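### Objective 2 is to test safety, but the SAP plans no heparin-versus-placebo estimate of harm; the larger gap is the adverse-event table

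*SAP*

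**What the plan says.** The objective, in SAP Sections 2.2 and 6.2, reads "To test the safety of intranasal heparin for treatment of adult and child outpatients with SARS-CoV-2 infection". It has two measures.

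- **Measure 2.1** is "The number of participants who discontinue treatment prior to day 10 from randomisation as a measure of treatment tolerability". Section 6.2 says "No statistical comparison will be made between the treatment arms" and continues "We will simply provide the proportion, with a 95% confidence interval, adjusted for clustering by household". The shell in Section 8, "Table 12: Secondary outcome 2: Safety of intranasal heparin", has a heparin and a placebo column and nothing for a comparison.
- **Measure 2.2**, in Section 2.2, is "Listing of adverse events and serious adverse events". Section 7 adds "Adverse events and serious adverse events will be summarised by treatment arm", with the mean duration of nose bleeds. The shell "Table 31: Adverse events" has n (%) for heparin and n (%) for placebo. It has no CI, no difference and no mention of households.

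By contrast, the primary outcome (Section 5.1), symptomatic disease (Section 6.3) and hospitalisation (Section 6.4) each get a risk ratio and a risk difference with 95% CI, and Tables 8, 13 and 15 have a comparison column.

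**The concern.** The placebo arm is what separates an effect of heparin from an effect of a saline spray or of COVID-19 itself. Several events named in Section 7, such as sneezing and nasal irritation, could come from any of the three. Only the between-arm contrast isolates the drug, and the plan does not report it for any harm.

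Two percentages show the direction of a difference but not how large an excess the data still allow. Benefit gets an effect size with its uncertainty; discontinuation, nose bleeds and other local reactions do not. Household clustering is recognised for discontinuation but not for adverse events, although each household is allocated to one arm as a whole.

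**Working it through.** **1. What each safety measure yields**

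| Measure | Per-arm figure | Per-arm CI | Clustering | Between-arm estimate |
|---|---|---|---|---|
| Discontinuation (6.2, Table 12) | proportion | yes | yes | ruled out |
| Adverse events, SAEs (7, Table 31) | n (%) | none | none | none specified |
| Hospitalisation (6.4, Table 15) | n (%) | yes | yes | RR and RD, but as COVID-19 severity |

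The last row is an efficacy outcome and does not fill the gap.

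**2. Inputs**

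The SAP gives no sample-size figure for safety. Section 2.6 gives the planned size: 120 households per arm, and 120 / 0.9 = 133.3, rounded up to 134; 134 × 4 = 536 persons per arm. Both figures reproduce. Section 2.6 also gives ICC 0.2, but for transmission. Assumptions here: event rates of 5 to 10%, and a safety ICC anywhere from 0 to 0.2.

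**3. Precision of a risk difference**

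Design effect DE = 1 + (4 − 1) × ICC, so 1.0 at ICC 0 and 1.6 at ICC 0.2. Effective n per arm is 536 / 1.6 = 335 at ICC 0.2. The 95% half-width is 1.96 × √(DE × [p0(1 − p0) + p1(1 − p1)] / 536).

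| Placebo, heparin | ICC 0 | ICC 0.2 |
|---|---|---|
| 5%, 5% | 2.6 points | 3.3 points |
| 5%, 10% | 3.1 points | 4.0 points |
| 10%, 10% | 3.6 points | 4.5 points |

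The 536 is inflated for loss and counts all household members, whereas the safety population is those older than 5 prescribed study drug. With 480 per arm (120 × 4), the range 2.6 to 4.5 becomes 2.8 to 4.8.

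**4. What a reader can recover**

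*Discontinuation.* Whole households are allocated, so the arms are independent and the half-width of the difference is about √(h0² + h1²). At 5% against 10% and ICC 0.2, h0 = 2.33 and h1 = 3.21, so √(5.43 + 10.30) = 3.97. The difference is 5.0 points (95% CI 1.0 to 9.0), the same as from the formula in step 3.

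*Adverse events.* From n (%) a reader can compute only an interval that ignores households. If the ICC were 0.2, that interval would be too narrow by a factor of √1.6 = 1.26: 3.1 points instead of 4.0 at 5% against 10%. Table 31 offers nothing to correct it with.

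**5. Do separate CIs mislead?**

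At 5% against 10%:
- ICC 0.2: per-arm CIs 2.7 to 7.3% and 6.8 to 13.2%. They overlap, yet the difference excludes zero (1.0 to 9.0).
- ICC 0: per-arm CIs 3.2 to 6.8% and 7.5 to 12.5%. They do not overlap, and the difference also excludes zero (1.9 to 8.1).

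The misleading pattern can occur, but it depends on the assumed rates and ICC.

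**The case against.** The strongest reply is that this is a deliberate and consistent choice. Measure 2.2 is defined as a listing, Section 6.2 names the per-arm proportion as its summary measure, and Tables 12 and 31 match. Descriptive safety reporting is common, and the verb in the objective is a stock opening used for most objectives in this SAP. All of that stands, and it is why no hypothesis test is asked for. Rewording the objective as describing safety would remove the mismatch, but it would still leave no estimate of harm.

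Three stronger readings are tempting and are not supported:

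- *A reader might infer that the SAP forbids any safety comparison.* The sentence in Section 6.2 belongs to measure 2.1. For adverse events a comparison is not forbidden; none is specified.
- *A reader might infer that nothing can be learned about the discontinuation difference.* The point difference is visible in Table 12 and its approximate interval follows from the two per-arm CIs (step 4).
- *A reader might infer that overlapping per-arm CIs will hide a real excess.* That rests on rates and an ICC the SAP does not give, and it fails at ICC 0 in the example. Nor does the SAP say overlap will be read as no difference.

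It is also fair that the gain is mostly for commoner local events. If major bleeding, heparin-induced thrombocytopenia or thrombosis prove very rare, n (%) remains the sensible display.

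Multiplicity is a weak defence. Section 3.5 makes no adjustment, and measure 5.1.1 with its 12-month repeat already plans 22 × 2 = 44 symptom odds ratios.

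**Conclusion.** The point holds as a worthwhile and cheap improvement, not as an error that threatens the trial. The SAP states a safety objective in placebo-controlled form and then plans no between-arm estimate for discontinuation, bleeding, local reactions or SAEs. The main gap is Section 7 with Table 31, which lacks a CI, a difference and any allowance for household clustering. The gap in Section 6.2 is smaller, because its interval can be approximated from what will be reported.

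At the planned size, a risk difference for events at 5 to 10% could be given to within about 2.6 to 4.5 points. This rests on 536 per arm, 4 per household, ICC 0 to 0.2 and Wald intervals; the rates and the safety ICC are assumptions. That the estimate is missing does not depend on them. No figure in the SAP is wrong on this point, and the efficacy analyses are untouched.

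**What to change.** 1. **Section 6.2.** Replace the sentence that rules out a comparison with: *The risk difference (heparin minus placebo) will be reported with a 95% CI using household-clustered standard errors, without a hypothesis test.*
2. **Section 7.** Specify the same estimate for the proportion of participants with at least one nose bleed, nasal irritation, nasal itching, sneezing, bleeding event or SAE. Keep n (%) only where events are very few, and state that threshold in advance.
3. **Tables 12 and 31.** Add a column for the risk difference with 95% CI.
4. Label these intervals as descriptive and unadjusted for multiplicity.

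The cost is a few sentences and one column in each of two tables, on data already planned for collection. The downside is several extra unadjusted intervals, of which one or two may exclude zero by chance; the descriptive label deals with that.

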6.3 Secondary outcome 3. Reduction of symptomatic disease

To test whether intranasal heparin administration reduces symptomatic disease in household members

Measure 3.1

Number of household contacts (swab negative on day 1 by PCR) becoming symptomatic of COVID-19 in next 28 days.

Symptomatic COVID-19 is defined as:

- Fever or chills PLUS ≥1 respiratory symptom (sore throat, cough, shortness of breath);
- OR 2 respiratory symptoms (sore throat, cough, shortness of breath);
- OR 1 respiratory symptom (sore throat, cough, shortness of breath) PLUS ≥2 non-respiratory symptoms (nausea or vomiting, diarrhea, headache, congestion or runny nose, sore throat, loss of taste or smell, myalgia, fatigue).

Symptoms are recorded as not present, mild, moderate or severe. A symptom will be regarded as being present if it is any of mild, moderate or severe.

Estimand

Population: Household contacts who test negative for SARS CoV-2 on day 1 by PCR

Treatment: Initially randomised intervention to unfractionated intranasal heparin 1400u each nostril (as heparin solution 5,000u/ml, 140microL/actuation, TWO actuations each nostril) THREE times daily via a plastic nasal inhalator device or saline control and any subsequent deviations to the per protocol use of the intervention over 10 days

Outcome: Becoming symptomatic of COVID-19 as defined above in the first 28 days.

Summary measure: Both relative (risk ratio) and absolute differences (risk difference) in proportions will be reported with 95% confidence intervals

Potential intercurrent events:

Index case in the household not taking study drug. This is defined as compliance <90% Participant (this household member) not taking study drug. This is defined as compliance <90% Either participant (this household member) or index case stop treatment due to adverse event Participant hospitalisation during first 10 days (removed from household) Participant received an anti-viral

Strategy for handling intercurrent event:

All intercurrent events will be handled through the treatment policy strategy, which means that the intercurrent events will be ignored.

The same analysis as described in Section 5.1 for the primary analysis will be done.

Measure 3.2

Days to symptom resolution for household members who were swab positive on day 1 by PCR, during the study period as measured with daily symptom diary until day 28.

Common symptoms included in the symptom diary are: Fever or chills, cough, shortness of breath or difficulty breathing, fatigue, muscle or body aches, headache, new loss of taste or smell, sore throat, congestion or runny nose, nausea or vomiting, diarrhea. The symptoms are measured as not present, mild, moderate or severe. Symptom resolution is defined as a symptom improving by at least 2 categories from its first measurement (on Day 1) or being not present. For example, a symptom measured as severe on Day 1 would be resolved if it measured mild, all other symptoms would be resolved if it changed from moderate to not present or from mild to not present. Symptom resolution had to be maintained for 2 consecutive days.

Estimand

Population: Household members who test positive for SARS CoV-2 on day 1 by PCR

Treatment: Initially randomised intervention to unfractionated intranasal heparin 1400u each nostril (as heparin solution 5,000u/ml, 140microL/actuation, TWO actuations each nostril) THREE times daily via a plastic nasal inhalator device or saline control and any subsequent deviations to the per protocol use of the intervention over 10 days

Outcome: Days from randomisation to the first day with symptom resolution. Participants who still have symptoms on day 28 will be censored on day 28 and regarded as not having symptom resolution. Participants who had no symptoms at randomisation, will be regarded as having 0 days to symptom resolution. **Summary measure**: Median days to symptom resolution in each treatment arm. Hazard ratio. If all participants are symptom free at the end of follow-up, we will be able to estimate the difference in mean days to resolution of symptoms between the arms

Potential intercurrent events:

Index case in the household not taking study drug. This is defined as compliance <90% Participant (this household member) not taking study drug. This is defined as compliance <90% Either participant (this household member) or index case stop treatment due to adverse event Participant received an anti-viral

Strategy for handling intercurrent event:

All intercurrent events will be handled through the treatment policy strategy, which means that the intercurrent events will be ignored.

Days to symptom resolution will be calculated from baseline to the first (of 2 consecutive days) day with symptom resolution (as defined above) for each of the symptoms individually. Participants who still have symptoms at the last time point will be censored at the time of last symptom checklist completed. Participants who are lost to follow-up will be censored at the last time a checklist was completed. The same analysis as described in Section 6.1 for endpoint 1.4 will be done.

In addition, an analysis for resolution of all symptoms will be done. This will be defined as the first day with all symptoms either mild or not present, maintained for 2 consecutive days. The analysis will be done in the same manner as for each individual symptom.

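### SAP Section 6.3: Measure 3.1 lists sore throat in two categories and uses a different symptom list from Section 2.2, and the resolution rules of Measure 3.2 do not fit together

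*SAP*

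**What the plan says.** **Measure 3.1.** SAP Sections 2.2 and 6.3 both give three routes to symptomatic COVID-19: fever or chills with at least one respiratory symptom; two respiratory symptoms; or one respiratory symptom with at least two non-respiratory ones. In both sections the respiratory symptoms are sore throat, cough and shortness of breath. The third route differs:

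- Section 6.3: "PLUS ≥2 non-respiratory symptoms (nausea or vomiting, diarrhea, headache, congestion or runny nose, sore throat, loss of taste or smell, myalgia, fatigue"
- Section 2.2: "PLUS ≥2 non-respiratory symptoms (chills, nausea, vomiting, diarrhea, headache, conjunctivitis, myalgia, arthralgia, loss of taste or smell, fatigue or general malaise"

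Under Section 6.3 any grade, even mild, makes a symptom present.

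**Measure 3.2.** The population is "Household members who test positive for SARS CoV-2 on day 1 by PCR". The rule for one symptom reads "Symptom resolution is defined as a symptom improving by at least 2 categories from its first measurement (on Day 1) or being not present". In the worked example severe to mild is a resolution, while "all other symptoms would be resolved if it changed from moderate to not present or from mild to not present". Resolution must hold for two days in a row, and times are derived separately for each of the 11 diary symptoms. The estimand adds three statements:

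- The day-28 rule: "Participants who still have symptoms on day 28 will be censored on day 28 and regarded as not having symptom resolution"
- The 0-day rule, for people free of symptoms at the start: "Participants who had no symptoms at randomisation, will be regarded as having 0 days to symptom resolution"
- The condition for a mean difference: "If all participants are symptom free at the end of follow-up, we will be able to estimate the difference in mean days"

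Section 6.3 then adds an all-symptom analysis. Its event is the first of two consecutive days on which no symptom is worse than mild, and it is to be analysed like the single symptoms.

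**The concern.** For 3.1, a route that asks for one respiratory and two non-respiratory symptoms can be met by two symptoms if sore throat is counted on both sides. The two sections also disagree on which non-respiratory symptoms count. Whether a contact with few symptoms is a case then depends on the section followed and on how the duplicate is read.

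For 3.2, a composite called resolution can be reached while none of its component symptoms has resolved. The censoring and mean-difference sentences are worded in terms of having symptoms, but both rules can be met with a symptom still present. In addition, nothing limits a symptom's analysis to people who have that symptom, so its median time mixes recovery with never having been affected.

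Measure 3.1 is reported as a risk ratio and risk difference, and 3.2 as medians and a hazard ratio. Two analysts could derive different outcomes from this text, and a choice made after seeing data would no longer be pre-specified.

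**Working it through.** The SAP states no figure on this point, so there is none to reproduce. The checks compare the rules over all possible symptom patterns.

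**1. Measure 3.1 on the diary items**

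Inputs: the 11 diary items listed under Measure 3.2. They comprise 3 respiratory items, fever or chills (1), congestion or runny nose (1), and 6 items on both non-respiratory lists (nausea or vomiting, diarrhoea, headache, muscle aches, loss of taste or smell, fatigue). That gives 2^11 = 2,048 present/absent profiles.

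The 2.2 list also has conjunctivitis, arthralgia and general malaise, which are not diary items. It has chills too, but chills with a respiratory symptom already qualify by the first route.

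Common to both definitions:
- two or more respiratory symptoms: (3 + 1) × 2^8 = 1,024
- exactly one respiratory symptom, with fever or chills: 3 × 2^7 = 384

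Exactly one respiratory symptom, without fever or chills:
- Section 2.2, at least two of 6, congestion free to vary: 3 × 2 × (64 − 1 − 6) = 342
- Section 6.3, sore throat counted once, at least two of 7: 3 × (128 − 1 − 7) = 360
- Section 6.3 read literally: cough or shortness of breath 2 × 120 = 240, plus sore throat with at least one of 7, 128 − 1 = 127; together 367

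| Definition | Qualifying profiles of 2,048 |
|---|---|
| Section 2.2 | 1,024 + 384 + 342 = 1,750 |
| Section 6.3, sore throat once | 1,024 + 384 + 360 = 1,768 |
| Section 6.3, literal | 1,024 + 384 + 367 = 1,775 |

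The duplicate adds 1,775 − 1,768 = 7 profiles: sore throat with exactly one of the 7 other listed items. Congestion or runny nose adds 1,768 − 1,750 = 18: 3 respiratory × 6 shared items. No diary profile qualifies only under 2.2. The 25 differences all have two symptoms (6 v 13 of 55 qualify) or three (91 v 109 of 165).

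**2. Measure 3.2, the rules side by side**

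Let d be the Day 1 grade (1 to 3) and c the current grade (0 to 3), which gives 12 pairs. The single-symptom rule is c = 0 or d − c ≥ 2. The all-symptom rule, for someone with only that symptom, is c ≤ 1. The pairs that end at mild are:

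| Day 1 to now | Single-symptom rule | All-symptom rule | Symptom still present |
|---|---|---|---|
| mild to mild | not resolved | resolved | yes |
| moderate to mild | not resolved | resolved | yes |
| severe to mild | resolved | resolved | yes |

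The two rules disagree on 2 of 12 pairs. In the third row they agree, yet the day-28 sentence would class the person as unresolved, and the symptom-free condition for the mean difference would fail. A person with only mild symptoms for all 28 days reaches the composite at the first assessment and is censored on each of those symptoms.

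**3. Measure 3.2, people without the symptom**

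Absence counts as resolved and the population is every Day 1 PCR positive. A member who lacks a symptom on Day 1, and still lacks it on the next diary day, therefore resolves it at about day 0. Let a share p of an arm be in that position. The SAP gives no value, so p is an assumption. With no censoring before the median, the arm's median is the (0.5 − p)/(1 − p) quantile among the rest:

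- p = 0.2: 0.3/0.8, the 37.5th percentile
- p = 0.3: 0.2/0.7, the 28.6th percentile
- p = 0.4: 0.1/0.6, the 16.7th percentile
- p = 0.5 or more: about day 0

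**The case against.** On 3.1, Section 2 is a synopsis and an analyst would naturally follow Section 6.3. The duplicate matters only if one symptom is counted as two; if symptoms must be distinct, the total is 1,768 whether or not sore throat is deleted from the second list. This stands as a limit on size. It does not remove the problem: the text does not say that symptoms must be distinct, and both lists stand in the same SAP. Section 2.8 says that departures from the protocol were made to resolve inconsistencies, but this one is internal to the SAP.

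A reader might infer that the 6.3 list is simply wider than the 2.2 list. The text does not support that. Section 6.3 adds sore throat and congestion or runny nose, but drops chills, conjunctivitis, arthralgia and general malaise. If every named item were recorded separately, 132 patterns would qualify only under 2.2 and 36 only under 6.3. The wider reading holds only for the diary items. The diary list appears under 3.2, and Section 2.7 also describes phone calls at days 14 and 28 to find who became symptomatic.

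On 3.2, the composite is introduced as an additional analysis with its own definition, and analysing it in the same manner may mean only the same survival model. A different threshold is not in itself a contradiction. That is fair, and relabelling is therefore enough. A reader might also infer that the sentences on remaining symptoms conflict with the composite alone. They do not: severe to mild shows that they fit the single-symptom rule no better.

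Finally, the 0-day sentence speaks of people with no symptoms at all, and the worked examples all start from a symptom that is present. Entry at about day 0 of people who lack one symptom is thus inferred and never stated. The inference holds even on that narrow reading, because the population is unrestricted and absence counts as resolved.

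**Conclusion.** The point holds and should be corrected before analysis. The double listing of sore throat, the disagreement between Sections 2.2 and 6.3, and the disagreement between the two resolution rules can all be read directly from the SAP. The entry of unaffected people at about day 0 follows from the rules as written.

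The sizes rest on assumptions. The 3.1 counts assume scoring from the diary and weight every profile equally, so they say nothing about how many contacts would be reclassified. The shift in the 3.2 medians depends on an unknown p.

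A reader might infer that the treatment comparison is biased. The SAP gives nothing from which the size or direction of a between-arm bias could be computed, and the effect on the hazard ratio has not been quantified here. The primary outcome and the other secondary measures are not touched by this point.

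**What to change.** **Measure 3.1.** List sore throat once, as respiratory. Use one list of symptoms that are actually recorded in both Section 2.2 and Section 6.3, and state whether congestion or runny nose belongs to it. On diary data that would be the only remaining difference: without it, 6.3 gives the same 1,750 profiles as 2.2.

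**Measure 3.2.**
- Reword the censoring sentences to refer to participants who have not met the resolution definition. Make the mean-difference summary conditional on all participants having met that definition.
- Name the composite for what it measures, all symptoms mild or absent. Keep it covering every symptom, including those that begin after Day 1, and limit it to people above that threshold on Day 1. Alternatively, reconcile it with the single-symptom rule.
- Run each single-symptom analysis in people who have that symptom on Day 1.

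The cost is SAP wording and derivation code. The single-symptom sets become smaller, as does the composite set if restricted, so estimates are less precise. Symptoms that start after Day 1 would be captured by the composite and not by the single-symptom analyses.
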